6.5 Concomitant medications

6.5.1 Permitted concomitant therapy for all treatment groups

Medications required to treat AEs, manage cancer symptoms, concurrent diseases and supportive care agents, such as packed red blood cells (PRBCs), pain medications, anti-emetics, short courses of steroids, chronic use of a low dose steroid for physiologic replacement, topical treatments for stomatitis and anti-diarrheal are allowed. The use of any other potential new concomitant medications may be discussed between the investigator and the sponsor on a case by case basis.

The patient must be told to notify the investigational site about any new medications he/she takes after the start of the study drug combination. All medications (other than study drugs) and significant non-drug therapies (including vitamins, herbal medicines, physical therapy and blood transfusions) administered within 30 days of study entry and during the study must be listed on the Concomitant medications/Significant non-drug therapies eCRF.

Patients taking concomitant medication chronically should be maintained on the same dose and dose schedule throughout the study period, as medically feasible.

Refer to the ([LEE011 Investigator's Brochure](#)), ([everolimus Investigator's Brochure](#)), ([aromasin package insert](#)) and ([Appendix 1 for concomitant medications](#)).

6.5.1.1 Hematopoietic growth factors

The use of Transfusions or Hematopoietic growth factor support (e.g. erythropoietins, G-CSF and GM-CSF) should be according to ASCO guidelines.

6.5.1.2 Bisphosphonates and denosumab

Bisphosphonates and denosumab are generally allowed with the following comments:

- Bisphosphonate/denosumab therapy for the treatment of osteoporosis is permitted.
- Bisphosphonate/denosumab therapy for the prevention of skeletal related events for patients with existing bone metastases is permitted.
- If bisphosphonate therapy is to be started after the first dose of study drug, prior consultation and approval by Novartis is required and the reason for its use must be clearly documented.

6.5.1.3 Palliative radiotherapy

Palliative radiation is permitted while on study after discussion with sponsor. It should not be delivered to a target lesion and it should not encompass more than 25% of irradiated bone marrow.

If palliative radiotherapy is initiated after the start of study treatment, the reason for its use must be clearly documented and progression as per RECIST 1.1 must be ruled out.

No dose modification of study treatment is needed during palliative radiotherapy.

6.5.1.4 Use of antiemetic medications

Ribociclib has low to minimal emetogenic potential according to the definition of antineoplastic agent emetogenicity (Grunberg et al 2010). Antiemetic therapy can be used according to clinical guidelines for antineoplastic medications with low to minimal emetogenic potential for treatment and/or prevention of nausea and vomiting as a result of study treatment (NCCN Clinical Practice Guidelines in Oncology. Antiemesis, 2017; Roila F et al 2016).

Potential drug interaction between ribociclib and antiemetic medications should always be taken into consideration. Example of a prohibited antiemetic medication is ondansetron that in combination with ribociclib may precipitate TdP. Refer to Appendix 1 for list of medications that are prohibited or allowed to be used with ribociclib.

6.5.2 Prohibited concomitant therapy during combined ribociclib + everolimus + exemestane

The following medications are prohibited during study treatment in the study (see [Table 14-1 in Appendix 1](#), this list is not comprehensive and is only meant to be used as a guide. Please contact the medical monitor with any questions):

- Strong and moderate inhibitors or inducers of CYP3A4/5.
- Substrates of CYP3A4/5 with a narrow therapeutic index.
- Medications with a known risk for QT prolongation.
- Other investigational and anti-neoplastic therapies, including chemotherapy, immunotherapy, target therapy, biological response modifiers, or endocrine therapy other than exemestane.
- Hormone replacement therapy, topical estrogens (including any intra-vaginal preparations), megestrol acetate and selective estrogen-receptor modulators (e.g. raloxifene).
- Prolonged systemic corticosteroid treatment (≥ 2 weeks), except for topical applications (e.g. rash), inhaled sprays (e.g. obstructive airways diseases), dexamethasone mouthwash (provided by Novartis), eye drops or local injections (e.g. intraarticular) should not be given. A short duration of systemic corticosteroids is allowed (e.g. chronic obstructive pulmonary disease, LFT abnormality).
- Herbal preparations/medications (except for vitamins) or dietary supplements that are strong inhibitors or inducers of CYP3A4/5 or those with a known risk of QT prolongation,

including, but not limited to: St. John's wort, Kava, ephedra (ma huang), gingko biloba, dehydroepiandrosterone (DHEA), yohimbe, saw palmetto, black cohosh and ginseng. Patients should stop using these preparations at least 7 days prior to first dose of study treatment.

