6.2.4.1 Ribociclib, everolimus and exemestane administration

Detailed instructions regarding administration of ribociclib capsules/tablets will be supplied to Investigator sites in a separate document from this protocol.

Complete guidelines for management and administration of exemestane can be found in ([Section 6.4](#)) and the package insert.

Ribociclib, everolimus and exemestane should be taken as follows:

- Patients should be instructed to take the study drug combination of one or more capsules/tablets of ribociclib with one tablet of everolimus and one tablet of exemestane with a large glass of water (~250 mL) daily approximately the same time every day.
- Patients should be instructed to swallow the ribociclib capsules/tablets and everolimus and exemestane tablets whole and not to chew, crush or open them.
- Patients should take all three drugs after eating a light low fat meal
- On days when PK collection/ECG is scheduled at the clinic, patients will take ribociclib, everolimus and exemestane in the clinic under the supervision of the investigator or designee. On all other days patients will take the ribociclib, everolimus and exemestane combination at home.
- If vomiting occurs during the course of treatment, no re-dosing of the patient is allowed before the next scheduled dose. The occurrence and frequency of any vomiting and/or diarrhea (or increase stool frequency) during a treatment cycle must be noted in the adverse events section of the eCRF.
- Any doses that are missed (not taken within 6 hours of the intended time) should be skipped and should not be replaced or made up on a subsequent day.
- Patients must avoid consumption of grapefruit, Seville oranges, grapefruit hybrids, pomelos, star fruit or products containing the juice of each during the entire study and preferably 7 days before the first dose of study medications, due to potential CYP3A4 interaction with the study medications. Orange juice is allowed.

- Herbal or dietary supplements known as strong inhibitors or inducers of CYP3A4/5 or those with a known risk of QT prolongation are not permitted. Multivitamins are permitted. If the potential for interactions are unknown, then the herbal / dietary supplements should be avoided.

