6.5.3 Permitted concomitant therapy requiring caution and/or action while on study

Permitted medications to be used with caution combined ribociclib + everolimus + exemestane treatment in this study ([Appendix 1, Table 14-2](#)) are listed below. These medications should be excluded from patient use if possible. If they must be given based on the investigator's judgment, then use with caution and consider a ribociclib interruption if the concomitant medication is only needed for a short time:

- Moderate inhibitors or inducers of CYP3A4/5.
- Sensitive substrates of CYP3A4/5 that do not have narrow therapeutic index.
- Strong inhibitors of BSEP.
- Medications that carry a possible risk for QT prolongation.
- Sensitive substrates of the renal transporters, MATE1 and OCT2.
- Sensitive substrates of BCRP (has a potential to increase exposure to substrates of these transporters, although no animal or clinical data are available to support these statements)

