7.1.4 Discontinuation of study treatment

Patients **may** voluntarily discontinue from the study treatment for any reason at any time. If a patient decides to discontinue from the study treatment, the investigator must make every effort (e.g. telephone, e-mail, letter) to determine the primary reason for this decision and record this information in the patient's chart and on the appropriate eCRF pages. They may be considered withdrawn if they state an intention to withdraw, fail to return for visits, or become lost to follow-up for any other reason.

The investigator should discontinue study treatment for a given patient if, on balance, he/she believes that continuation would be detrimental to the patient's well-being.

Patients may be withdrawn from the study treatment if any of the following occur:

- Adverse Event
- Lost to follow-up
- Physician decision
- Progressive Disease
- Protocol deviation
- Study terminated by sponsor
- Technical problems

Patients must be withdrawn from the study treatment if any of the following occur:

- Pregnancy

- Death
- Subject/Guardian decision

In addition to the general withdrawal criteria, the following study specific criteria will also require study treatment discontinuation:

- Adjustments to study treatment that result in discontinuation. Please refer to [Section 6.4](#).
- Use of prohibited medication. Please refer to [Section 6.5](#) and [Appendix 1](#).

Patients who discontinue study treatment should NOT be considered withdrawn from the study. They should return for the assessments indicated in [Table 7-1](#). If they fail to return for these assessments for unknown reasons, every effort (e.g. telephone, email, letter) should be made to contact them as specified in [Section 7.1.8](#).

Patients who discontinue study treatment should undergo an End of Treatment (EOT) visit followed by a 30 day safety follow-up.

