14.1 Appendix 1- Concomitant medication

In general, the use of any concomitant medication deemed necessary for the care of the patient is permitted in this study, except as specifically prohibited below. Combination administration of study drugs could result in drug-drug interactions (DDI) that could potentially lead to reduced activity or enhanced toxicity of the concomitant medication and/or ribociclib.

The following lists are based on the Oncology Clinical Pharmacology Drug-Drug Interaction and Co-Medication Considerations (v05 release date: 2015), which was compiled from the Indiana University School of Medicine's "Clinically Relevant" Table (<http://medicine.iupui.edu/clinpharm/ddis/main-table/>) and supplemented with the FDA Draft Guidance for Industry, Drug Interaction Studies – Study Design, Data Analysis, and Implications for Dosing and Labeling (February 2012) (<http://www.fda.gov/downloads/drugs/guidancecomplianceregulatoryinformation/guidances/u/cm292362.pdf>), and the University of Washington's Drug Interaction Database ([.druginteractioninfo.org/](http://druginteractioninfo.org/)). For current lists of medications that may cause QT prolongation and/or torsade's de pointes (TdP), refer to the CredibleMeds® website (www.qtdrugs.org/).

These lists are not comprehensive and are only meant to be used as a guide. Please contact the medical monitor with any questions.

Table 14-1 List of prohibited medications during study drug treatment

Category	Drug Name
Strong CYP3A4/5 inhibitors	Atazanavir/ritonavir, boceprevir, clarithromycin, cobicistat, conivaptan, danoprevir/ritonavir, elvitegravir/ritonavir, grapefruit juice, indinavir/ritonavir, itraconazole, ketoconazole, lopinavir/ritonavir, mibefradil, nefazodone, nelfinavir, posaconazole, ritonavir, saquinavir, saquinavir/ritonavir, telaprevir, telithromycin, tipranavir/ritonavir, troleandomycin, voriconazole
Strong CYP3A4/5 inducers	Carbamazepine, lumacaftor, mitotane, phenobarbital, phenytoin, rifabutin, rifampin (rifampicin) ³ , St. John's wort (hypericum perforatum) ³ , enzalutamide
CYP3A substrates with NTI ¹	Alfentanil, astemizole, cisapride, cyclosporine, diergotamine (dihydroergotamine), ergotamine, fentanyl, lomitapide ⁵ , lovastatin, nicardipine, nisoldipine, pimozide, quinidine, simvastatin, sirolimus, tacrolimus

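### Protocol 6.5.2 prohibits moderate CYP3A4/5 inhibitors and inducers that 6.5.3 and Table 14-2 permit with caution, so the mandatory stop in 7.1.4 has two readings; most of the text points to strong agents only

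*Protocol*

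**What the plan says.** Section 6.5.2 gives the treatments that are prohibited during study treatment. Its first bullet is "Strong and moderate inhibitors or inducers of CYP3A4/5". The section refers to Table 14-1, says that the list is only a guide and not comprehensive, and sends questions to the medical monitor.

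Section 6.5.3, whose title begins with the word permitted, has as its first bullet "Moderate inhibitors or inducers of CYP3A4/5". Its introduction says "These medications should be excluded from patient use if possible". If the investigator judges that such a drug must be given, it is used with caution, and a ribociclib interruption is considered when the need is short.

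Appendix 1 follows the same split as 6.5.3. The prohibited list, Table 14-1, has a row for "Strong CYP3A4/5 inhibitors" and one for strong inducers, with no moderate row. The caution list, Table 14-2, has one row for moderate inhibitors and one for moderate inducers.

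Section 7.1.4 states that "the following study specific criteria will also require study treatment discontinuation". One of those criteria is "Use of prohibited medication", with a reference to Section 6.5 and to Appendix 1.

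**The concern.** One class of drug is prohibited in one section and permitted with caution in the next. This matters because a mandatory stopping rule hangs on the word prohibited, and that rule cites both sources without saying which governs.

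Both directions carry a cost. If only strong agents were meant, a site that follows 6.5.2 literally would take a patient with advanced breast cancer, possibly one who is benefiting, off study treatment without need. If the stricter rule was meant, a site that follows 6.5.3 would keep a patient on a combination that the sponsor intended to avoid. Ribociclib prolongs QT in a concentration-dependent way (Amendment 3 rationale), its elimination may be affected by CYP3A4 inhibitors or inducers (1.2.1.2), and everolimus is a sensitive CYP3A4 substrate (1.2.5.1.1).

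A lesser matter is deviation coding. SAP 2.3.1 records use of the prohibited substances it covers as protocol deviations, so sites and the database could classify the same use differently.

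**Working it through.** No figure in the plan depends on this, so the check sets the texts side by side.

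**Step 1: is the conflict in the current text?** Yes. Both bullets stand in the body of the protocol. The Amendment 3 change list records edits to 6.5.2, 6.5.3 and both Appendix 1 tables, and both rules are still present.

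**Step 2: what happens to a patient who needs, say, diltiazem or verapamil?** Both are in the moderate-inhibitor row of Table 14-2.
- Under 6.5.2 with 7.1.4: prohibited, so study treatment must stop.
- Under 6.5.3 with Table 14-2: allowed with caution, perhaps with ribociclib interrupted.

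**Step 3: which reading does the rest of the protocol support?**
- Appendix 1 opens with a default: medication deemed necessary for the patient's care is allowed unless specifically prohibited in what follows. Table 14-1 then bars only strong CYP3A4/5 inhibitors and inducers.
- Section 1.2.1.4.4 gives the clinical interaction data. Ritonavir, a strong inhibitor, raised ribociclib AUCinf 3.2-fold, and rifampicin, a strong inducer, lowered it by 89%. The conclusion drawn there is that strong inhibitors and strong inducers are prohibited.
- Section 6.2.4.1 bars "Herbal or dietary supplements known as strong inhibitors or inducers of CYP3A4/5".
- The herbal bullet in 6.5.2 itself bars herbal preparations or "dietary supplements that are strong inhibitors or inducers of CYP3A4/5". Yet two plant products (asafoetida resin and Schisandra) are in the moderate-inhibitor row of Table 14-2. On CYP strength, the first 6.5.2 bullet bars them and the herbal bullet does not.
- Exclusion criterion 25 names strong agents only, though it governs eligibility and not treatment.
- SAP 2.3.1 does not mention moderate agents, but it is weak evidence, because the SAP says it was prepared from the original protocol.

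These point to strong agents only.

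**Step 4: does any of this formally override 6.5.2?** No. Section 6.5.2 calls the Table 14-1 list not comprehensive, so the absence of a moderate row does not cancel the bullet. The protocol states no order of precedence.

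**Step 5: how many named agents are involved?** Table 14-2 names 14 moderate inhibitors and 9 moderate inducers: 14 + 9 = 23. None of the 23 appears on its own in Table 14-1. The only overlap is lopinavir, which is prohibited there in combination with ritonavir, as footnote 5 of Table 14-2 confirms. Some of the 23 may be barred by another 6.5.2 bullet, such as the one on anti-neoplastic therapy. The documents do not classify them, so no smaller figure is given.

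**Step 6: what would deviation coding catch?** SAP Table 2-1 is not confined to strong CYP3A4/5 agents. It also covers narrow-index substrates, drugs with a known QT risk, herbal preparations and antineoplastic therapy. It names aprepitant, one of the 23, as a narrow-index substrate. The SAP's update rule points to the most recent prohibited list, and the current Table 14-1 does not name aprepitant. The gap is therefore limited to moderate agents not listed on other grounds: 6.5.2 calls them prohibited, but neither list would flag them.

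**The case against.** The strongest reply is that this is an editorial slip with little practical reach. The Appendix 1 default addresses the case where a drug is necessary, which is the only case where the rules part. Section 6.5.1.4 sends sites to Appendix 1 for what is prohibited or allowed, at least for antiemetics. Section 6.5.3 already says to avoid these drugs where possible, the medical monitor takes questions, and 6.5.1 allows other new medications to be discussed with the sponsor case by case. SAP Section 4 records 46 + 33 = 79 Phase II patients as already recruited, so only those still on treatment can be affected.

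Much of this stands. It shows which reading is likely to be right and that the occasions are limited. It does not remove the conflict. The monitor can advise on one patient, but Section 12 permits no authorized deviations and 12.1 requires a written amendment to change the protocol. Two sites can each follow the text and reach opposite decisions on stopping.

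A reader might also infer that the intent is wholly open, so that the two rules are equally likely. The documents do not support that. The QT and CYP3A4 statements could justify a stricter rule, but none of them says that moderate agents should be barred, while the texts in Step 3 name strong agents.

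**Conclusion.** The protocol contradicts itself on moderate CYP3A4/5 inhibitors and inducers, and the contradiction reaches a required treatment stop. The weight of the text favours prohibiting strong agents only. That is an inference about intent, which the sponsor should confirm, because nothing formally overrides 6.5.2.

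The size is small and cannot be put in patients. The rules diverge only when a moderate agent is judged unavoidable, and the documents give no frequency of use. A reader might take the 23 named agents as the extent of the problem. It is a count of names under a class label, and some of those names may be barred on other grounds.

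Two further inferences are not supported. The first is that deviation coding would miss every moderate agent: SAP Table 2-1 covers several other categories and lists aprepitant. The second is that the primary result is at risk. The primary analysis uses the full analysis set, defined by having received the assigned combination, and no effect on the clinical benefit rate is claimed. The per-protocol set excludes major violations, but the documents do not say that use of a moderate agent would be one, so no effect on that set is claimed either.

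**What to change.** **Preferred.** In the next amendment, delete the words *and moderate* from the first bullet of 6.5.2. Section 6.5.3 and Tables 14-1 and 14-2 then stand as written and agree with 6.2.4.1 and the herbal bullet.

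**Only if the sponsor confirms that the stricter rule was intended.** Delete the moderate bullet from 6.5.3 and move the two moderate rows from Table 14-2 to Table 14-1. The update rule in SAP 2.3.1 would then bring those agents into deviation coding without a separate rule.

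Until the amendment is approved, sites should refer any unavoidable moderate agent to the medical monitor, whom 6.5.2 already names for questions.

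**Cost.** One written amendment, approved by the sponsor, the ethics board and health authorities where required (12.1). It can be combined with other changes and needs no new data collection. The preferred change gives up the stricter wording; the alternative may take some patients off treatment. The benefit is limited to patients still on treatment and to consistent deviation coding.
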